3.0 STUDY POPULATION

3.1 Entrance Criteria

Twenty healthy adult patients (10 in each group) of any ethnicity or gender whose treatment plan includes extraction of maxillary anterior teeth and/or mandibular and/or maxillary pre-molars and their replacement with root-form dental implants will be consecutively recruited for enrollment in the study.

Participants must be at least 19 years old with demonstrated ability to understand the proposed treatment recommendations and prognosis and be able to provide informed consent, in English, without the aid of ad-hoc translation from another language. Decisionally-impaired adults and/or minors, who cannot consent for themselves, will not be enrolled; women who are pregnant or lactating at the time of enrollment will not be included. Women will be tested for current pregnancy status.

Prior to enrollment, prospective participants must agree to be available for the entire duration of the study, be compliant with needed study-related evaluations and demonstrate a willingness to comply with strict time-line requirements. Certain health and medication exclusions apply (table 1).

Table 1 Entrance Criteria

Inclusion	Exclusion
Existence of one or more non-adjacent teeth in the aesthetic zone that are scheduled for extraction	Pregnancy or lactating at the time of enrollment
Healthy enough to undergo the proposed therapy without compromise to their existing health status	Previous malignant neoplasm
Demonstrated willingness to comply fully with protocol time-line and procedural requirements	A known hypersensitivity to DBM
At least nineteen years old	A known hypersensitivity to Titanium metal
Able to read and understand written English without the aid of ad hoc interpretation	Any health condition that in the opinion of the clinical investigators may adversely affect bone healing
Able to cognitively understand the proposed study therapy and possible prognosis	Any medication that in the opinion of the clinical investigators may adversely affect bone healing
Able to consent for their own inclusion in the study	Any indication of an inability to make autonomous decisions

3.2 Visit Sequence

The study will include a minimum of four time-sensitive clinic visits over seven consecutive weeks; dental implants will be placed 8 weeks after extraction/grafting procedures. Following implant

placement, additional visits, necessary for health maintenance will be completed. Implants will be uncovered following routine practice and at the investigator's discretion. The implants will be restored and the number and sequence of visits will be scheduled at the restoring dentist's discretion. Participants will return for two follow-up visits at 12 and 24 months after permanent prosthetic attachment.

4.0 SUMMARY OF STUDY PROCEDURES

4.1 Enrollment and Treatment Planning

After completing an individualized, private consent discussion and obtaining informed consent, a pre-surgical assessment will be completed. Each enrolled participant will be seen for an initial evaluation to include assessments of medical and dental conditions that will verify compliance with entrance criteria and for collection of demographic data.

Participants will be assigned a unique identification number. Information will be recorded on baseline case report forms (CRFs) developed specifically for this study.

Each participant may have up to four non-adjacent sites selected for inclusion as study treatment sites. Through consultations with prosthodontic clinicians, the documented treatment plan will be reviewed and revised if necessary to develop a therapy that will be of most benefit to the participant.

4.2 Randomization

Participants will be stratified for smoking status and randomized to one of two extraction/grafting groups. In the case of multiple tooth sites within one participant, all the tooth sites will be assigned to receive the same graft material.

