	
Implants Exposed Mandibular implants will be exposed after approximately 4 months; maxillary implants will be uncovered after approximately 6 months.
 
Implant Restoration Implants will be restored in the conventional manner with aesthetically pleasing cemented single crown restorations by one of the investigators. Photographs and radiographs will be obtained at permanent restoration.
 
Longitudinal Follow-up Two annual follow-up evaluations will be completed at 12 months and 24 months from the date the permanent restoration is attached to the implant. Each assessment will include:
 
 Standardized intra-oral periapical dental radiographs Clinical photographs Measurement of clinical parameters Assessment of soft-tissue contours Assessment of overall aesthetics Assessment of implant/restoration interface
Population	
Twenty healthy adult patients (10 per group) of any ethnicity or gender whose treatment plan includes extraction of mandibular and/or maxillary pre-molars and/or maxillary anterior teeth and their replacement with root-form dental implants and who meet the entrance eligibility criteria will be consecutively recruited for enrollment in the study. See inclusion/exclusion criteria – Table 1.

Outcomes	
Histology and histomorphometric analyses (site biopsies)
 
Soft-Tissue aesthetic assessments (Jemp Indices and photographs)
 
Soft Tissue Health (PI & GI, and photographs)
 
Bone Support to Implants (standardized PA radiographs and image analysis)
 
Radiographic image analysis of osseous architecture changes at study sites over time

Statistical Analyses Plan	
Two-tailed t tests will be used to compare clinical characteristics between the test and control therapies for continuous variables with a normal distribution. Nonparametric (Wilcoxon) tests will be used otherwise.
 
For categorical variables, inter-group comparisons will be conducted using chi-square tests or Fisher's Exact Test, as deemed necessary.
 
To determine whether the groups experienced equivalent changes in bone growth from baseline to follow-up, paired t (or Wilcoxon signed-rank) and McNemar's tests will be used for continuous and categorical variables, respectively. The α level will be set at 0.05.
 
Statistical analysis will be carried out using SAS software version 9.2 (SAS Institute, Inc, Cary, North Carolina).

[figure not shown]

Table of Contents

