6.6 Implants Exposed

Implants will be exposed upon the investigator's determination that the implants are sufficiently integrated to withstand the forces of loading. In general, mandibular implants will be uncovered and restoration initiated approximately 4 months after placement; maxillary implants will be uncovered and restoration initiated approximately 6 months after placement.

Prior to exposing the implants subjects will be given a loading dose of antibiotics based on their medical history and concomitant medications. Local anesthesia will be achieved in the region by regional block or local infiltration. Conscious sedation may be added at the surgeon's discretion to help manage a patient's anxiety. The facial area will be scrubbed by 2% Chlorhexidine soap and the oral cavity disinfected by rinsing for 1 minute with a 0.12% chlorhexidine gluconate antimicrobial oral rinse prior to the procedure.

Once the treatment areas are sufficiently anesthetized a crestal incision will be made to reveal the top of the implant and an abutment will be attached. The incision will be closed with sutures and the temporary prostheses will be adjusted. Clinical photographs will be taken before, during and after the procedure; following the procedure and standardized intra-oral radiographic images of each implant site will be captured.

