13.4 Statistical Analysis Plan

Two-tailed t tests will be used to compare clinical characteristics between patients with the Bone Allograft (control therapy) and those with the Bone Allograft/Amnion Allograft (test therapy) for continuous variables with a normal distribution. Nonparametric (Wilcoxon) tests will be used otherwise.

For categorical variables, inter-group comparisons will be conducted using chi-square tests or Fisher's Exact Test, as deemed necessary. To determine whether the groups experienced equivalent changes in bone growth from baseline to follow-up, paired t (or Wilcoxon signed-rank) and McNemar's tests will be used for continuous and categorical variables, respectively.

The α level will be set at 0.05. Statistical analysis will be carried out using SAS software version 9.2 (SAS Institute, Inc, Cary, North Carolina).

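### Section 13.4 makes no adjustment for jaw, although the protocol expects slower implant integration in the maxilla; one prespecified covariate would help, most clearly for crestal bone

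*Combined protocol and SAP*

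**What the plan says.** Section 3.1 admits both jaws ("extraction of maxillary anterior teeth and/or mandibular and/or maxillary pre-molars") and sets the size: "Twenty healthy adult patients (10 in each group) of any ethnicity or gender". Section 4.2 allocates by participant and balances one factor: "Participants will be stratified for smoking status and randomized to one of two extraction/grafting groups". All sites in a participant get the same graft, and section 4.1 allows up to four sites.

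The jaws share one schedule up to implant placement: CBCT at week 7 (section 4.8), then biopsy and implant at week 8 (section 3.2: "dental implants will be placed 8 weeks after extraction/grafting procedures"). They separate afterwards. Section 6.6 makes uncovering depend on integration and gives the usual timing: "mandibular implants will be uncovered and restoration initiated approximately 4 months after placement; maxillary implants will be uncovered and restoration initiated approximately 6 months". The synopsis gives the same intervals.

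Sections 3.2, 8.0 and 9.1 and aim 8 in section 2.3 time the long-term visits at 12 and 24 months after restoration. Section 13.3 takes crestal bone change from the measurement at insertion.

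Section 13.4 begins: "Two-tailed t tests will be used to compare clinical characteristics between patients". It adds Wilcoxon, chi-square or Fisher, paired and McNemar tests. It names no covariate or stratified analysis, so neither jaw nor the stratification factor, smoking, enters the analysis. Jaw appears in no aim or outcome in sections 2.3 and 13.1 to 13.3.

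**The concern.** The protocol itself treats jaw as relevant to how bone takes up an implant. Jaw is known before randomisation, because Table 1 requires teeth already scheduled for extraction, and images are labelled with tooth number (section 9.3). With 10 participants per arm, chance can leave one arm with noticeably more mandibular participants. An unadjusted comparison then carries part of any jaw difference in the graft estimate. Even with balanced arms, variation between jaws stays in the error term. For crestal bone there is a second route: jaw shifts the time between the insertion baseline and each follow-up image.

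**Working it through.** The plan states no power, effect size, SD, jaw mix or jaw effect, so there is no figure to reproduce. From the documents: 20 participants, 10 per arm, two-sided 0.05. Assumed: one jaw per participant; 4 to 10 of 20 mandibular; a jaw effect of 0.5 to 1.5 within-jaw SD; allocation unrelated to jaw.

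**1. Chance imbalance.** With M mandibular participants, the number x in one arm is hypergeometric: P(x) = C(10,x)·C(10,M−x)/C(20,M). The arms differ by |2x − M|. The probability of a difference of at least 4 is:
- M = 4: 2(210)/4845 = 8.7%
- M = 6: 2(210 + 2520)/38760 = 14.1%
- M = 8: 2(45 + 1200 + 9450)/125970 = 17.0%
- M = 10: 2(1 + 100 + 2025 + 14400)/184756 = 17.9%

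If M is odd, the difference is odd too. For M = 5, at least 3 has probability 30.3% and at least 5 has 3.3%.

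**2. Shift in the estimate.** A difference of 4 is 4/10 = 40 percentage points, so the unadjusted difference moves by 0.4 × the jaw effect: 0.2, 0.4 or 0.6 SD for effects of 0.5, 1.0 or 1.5 SD. The standard error of the arm difference in within-jaw SD units is sqrt(2/10) = 0.45.

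**3. Type I error (20,000 simulated trials per setting, M = 6 and 10).** Overall, the unadjusted test rejects in 0.046 to 0.053 of trials. Among trials with an imbalance of at least 4, it rejects in about 0.06, 0.11 and 0.16 to 0.17 for jaw effects of 0.5, 1.0 and 1.5 SD. The test adjusted for jaw rejects in about 0.05.

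**4. Precision.** Adjustment multiplies the variance by (1 − R²)/(1 − r²), where R² is the share of outcome variance explained by jaw and r is the chance arm–jaw correlation. Under random allocation r² averages 1/19, so the standard-error ratio is about sqrt((1 − R²) × 19/18):

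| R² | adjusted/unadjusted SE |
|---|---|
| 0 | 1.03 |
| 5% | 1.00 |
| 10% | 0.97 |
| 20% | 0.92 |
| 30% | 0.86 |

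Simulation agrees to within about 0.01. Break-even is R² = 1/19 = 5.3%.

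With mandibular share p and jaw effect d, R² = p(1−p)d²/(1 + p(1−p)d²). For p = 0.3 and 0.5 this gives 5% to 6% at d = 0.5, 17% to 20% at d = 1.0, and 32% to 36% at d = 1.5.

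**5. Power.** Ten per arm detects 1.32 SD at 80% power (noncentral t, 18 df). At a true difference of 1.32 within-jaw SD, simulated power is:

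| jaw effect | unadjusted | adjusted |
|---|---|---|
| 0.5 SD | 0.78 | about 0.77 |
| 1.0 SD | 0.70 to 0.72 | about 0.77 |
| 1.5 SD | 0.60 to 0.63 | about 0.77 |

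**6. Time since placement.** Add time to uncovering (section 6.6), one to two months of restoration (section 7.0) and the visit interval (section 8.0):
- 12-month visit: mandible 4 + (1 to 2) + 12 = 17 to 18 months; maxilla 6 + (1 to 2) + 12 = 19 to 20 months.
- 24-month visit: 29 to 30 against 31 to 32 months.

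The gap is about two months. A 40-point jaw imbalance makes the arms' mean follow-up differ by 0.4 × 2 = 0.8 months.

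**The case against.** The strongest reply is that the 4- and 6-month intervals concern implant integration, not socket healing. Ridge dimensions, bone fill, histology and torque are all measured before those intervals begin, on one schedule for both jaws. That stands: a reader might infer that the protocol documents a jaw effect on every outcome, and it does not.

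A reader might also infer that the planned tests are invalid. They are not. Overall type I error stays near 0.05, and chance imbalance is part of what that error rate covers. The conditional bias is real only in the minority of allocations that come out unbalanced. With a 1 SD jaw effect and a 40-point imbalance, the shift (0.4 SD) is still below one standard error (0.45 SD).

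The size of the gain is assumed throughout, and at 0.5 SD there is none. Other baseline variables, such as socket-wall defects, could also be proposed. Jaw stands out because the protocol attaches its own timetable to it.

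Change from insertion removes fixed jaw differences in crestal level. It does not remove a difference in rate, or the extra two months. The two-month argument relies on the visit schedule in sections 3.2, 8.0 and 9.1. Sections 13.0 and 13.1 date the data from implant placement instead, and under that timing the gap disappears. The uncovering times are also approximate and left to discretion (sections 3.2 and 4.10).

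Finally, a reader might conclude that randomisation should be stratified by jaw. The documents do not support that step: smoking by jaw gives four small strata among 20 participants, and one participant may have sites in both jaws.

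**Conclusion.** The point holds as a low-cost improvement to the analysis plan, not as a flaw in the randomisation or in the validity of the planned tests. The trial mixes jaws, the protocol expects integration to differ by jaw, and section 13.4 uses neither jaw nor smoking. Support is best for crestal bone, where maxillary implants are measured about two months later after placement if visits run from restoration. For the 7- to 8-week outcomes, a jaw effect is plausible but undocumented.

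A 4-participant imbalance has probability 9% to 18% under the even jaw mixes examined. Adjustment loses about 3% in standard error if jaw explains nothing, breaks even at about 5% of variance, and gains about 8% at 20%. These figures rest on one jaw per participant and an assumed jaw effect. The randomisation table and Manual of Procedures were not in the text reviewed.

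**What to change.** Leave randomisation as it is. In section 13.4, prespecify for continuous outcomes (crestal bone, ridge dimensions, bone fill, histology, torque) a linear model with arm, jaw and smoking, the factor already used for stratification.

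Define jaw at baseline:
- **Histology:** the jaw of the biopsy site. Table 2 places both site selection and randomisation at V-1, so record the site before the allocation is known.
- **Other outcomes:** choose one rule in advance. Either use the proportion of the participant's sites enrolled at randomisation that are maxillary, or fit a site-level model with a jaw term and a participant random effect. Do not use the proportion among analysed sites: section 11.1 removes failed or too-narrow sites from the results, so the graft could change that covariate.

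Keep the planned unadjusted t or Wilcoxon test as a sensitivity analysis; this also retains the plan's route for non-normal outcomes. Implant survival and categorical outcomes are outside this change. Reconcile whether follow-up is timed from placement or restoration, since that decides whether the two-month gap exists.

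The cost is SAP wording and model terms using baseline information already available. Jaw takes one degree of freedom and about 3% in standard error if it has no effect; smoking adds a similar small cost. Prespecification matters, because adding jaw only after seeing an imbalance would be a data-driven choice.

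### Randomisation is stratified by smoking, but the planned between-group tests ignore the stratum, so participant-level comparisons lose power if smoking affects healing

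*Combined protocol and SAP*

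**What the plan says.** Section 4.2, and the Randomization row of the synopsis, make smoking the only stratification factor: "Participants will be stratified for smoking status and randomized to one of two extraction/grafting groups". Block size, method of allocation within strata and the expected number of smokers are not given. The participant is the unit of assignment, because with several teeth "all the tooth sites will be assigned to receive the same graft material". The sample is "Twenty healthy adult patients (10 in each group"), per section 3.1.

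Section 13.4, repeated in the synopsis, is the whole analysis plan. For normally distributed continuous variables: "Two-tailed t tests will be used to compare clinical characteristics between patients with the Bone Allograft (control therapy") and the test-therapy patients. Then: "Nonparametric (Wilcoxon) tests will be used otherwise". For the rest: "For categorical variables, inter-group comparisons will be conducted using chi-square tests or Fisher's Exact Test, as deemed necessary". For change from baseline, "paired t (or Wilcoxon signed-rank) and McNemar's tests will be used for continuous and categorical variables, respectively". The significance level is fixed: "The α level will be set at 0.05". No model, covariate or stratified test is named, and smoking does not appear in the aims, the endpoints or the analysis section.

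**The concern.** Stratifying on a factor is normally a statement that it may matter to the outcome; the protocol gives no reason of its own. When smokers are shared evenly between arms, smoking contributes nothing to the difference in means. A two-sample t test still counts the spread between smokers and non-smokers as error. Its standard error is then too large for the design, its p-values too high and its intervals too wide.

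With 10 participants per arm, only very large differences can be detected, so precision given away in the analysis is hard to recover.

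**Working it through.** **Inputs from the documents.** 20 participants, 10 per arm (section 3.1); two-sided tests at 0.05 (section 13.4); smoking the only stratum (section 4.2). The plan states no effect size, SD, power or sample-size calculation, so there is no figure of its own to reproduce.

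**Assumptions.** Participant-level normal outcome with SD 1 within each smoking stratum; 2, 4, 6 or 10 smokers of 20; smokers differ by b = 0, 0.5, 1 or 1.5 SD; true treatment effect 1.32 SD. That effect was chosen because the exact two-sample t test with 10 per arm then has power 79.7% when smoking is irrelevant.

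**Step 1: standard error.** With a proportion q of smokers in each arm:

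- true SE of the difference = √(2/10) = 0.447, because smoking cancels;
- expected pooled variance used by the t test = 1 + 20·q(1−q)·b²/18.

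For 6 smokers (q = 0.3) and b = 1: 1 + 20 × 0.21 / 18 = 1.233, and √1.233 = 1.11. The reported SE is about 0.447 × 1.11 = 0.497. In simulation the mean reported SE is 0.490 against a true 0.447, about 10% too wide.

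**Step 2: error rate and power, balanced strata.** Simulation with 200,000 runs per cell, comparing the two-sample t test (18 df) with a linear model of group + smoking (17 df):

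| Smoking effect | Smokers of 20 | Type I error, t test | Power, t test | Power, group + smoking |
|---|---|---|---|---|
| 0 | 2 to 10 | 5.0–5.1% | 79.6–79.8% | 79.4–79.5% |
| 0.5 SD | 2 | 4.7% | 79.0% | 79.5% |
| 0.5 SD | 10 | 4.4% | 77.7% | 79.4% |
| 1 SD | 2 | 4.1% | 76.8% | 79.5% |
| 1 SD | 4 | 3.5% | 74.5% | 79.4% |
| 1 SD | 6 | 3.1% | 72.8% | 79.5% |
| 1 SD | 10 | 2.8% | 71.3% | 79.3% |
| 1.5 SD | 2 | 3.1% | 73.1% | 79.3% |
| 1.5 SD | 4 | 2.2% | 67.7% | 79.4% |
| 1.5 SD | 6 | 1.7% | 64.1% | 79.4% |
| 1.5 SD | 10 | 1.5% | 61.3% | 79.6% |

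The linear model keeps type I error at about 5% throughout. Repeat runs move the error rates by about 0.1 point (2.7 to 2.8% for 10 smokers at 1 SD; 1.4 to 1.5% at 1.5 SD).

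**Step 3: balance within strata not enforced.** Same settings, but 10 per arm drawn without regard to smoking:

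- The t test's type I error is about 5% in every cell and its SE is about right (6 smokers, 1 SD: 0.487 reported, 0.495 true).
- At 1 SD the t test has power 76.0%, 73.4%, 71.7% and 70.0% with 2, 4, 6 and 10 smokers. The adjusted model has about 77%, so the loss is 1 to 7 points.
- At 1.5 SD the loss is about 6 to 17 points.
- At 0.5 SD the adjusted model is level or up to 1.7 points worse. With no smoking effect it is about 2.7 points worse, because chance imbalance has to be paid for.

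**Step 4: cost of the term under balance.** The critical t value goes from 2.101 (18 df) to 2.110 (17 df). With no smoking effect, power falls by about 0.3 points.

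**The case against.** The documents give no smoking effect, smoker count, outcome SD or target difference, so every power figure rests on assumptions. Section 3.1 enrols healthy adults and lets investigators exclude conditions that may impair bone healing, so smokers could be few; with 2 of 20 and a 1 SD effect the loss is under 3 points. With a weak smoking effect it is 2 points or less whatever the count. The error is conservative and leaves the estimate unbiased. All of this stands, and it makes the point one of efficiency rather than validity.

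Three stronger readings are tempting and are not supported.

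- *A reader might infer that every test in section 13.4 is affected.* The paired t, signed-rank and McNemar tests are within-group as written, so the argument about the between-arm standard error does not reach them.
- *A reader might infer that stratification alone makes the reported standard errors too wide.* That requires balance within strata, and section 4.2 does not say how, or whether, balance is enforced. Without it only the power loss remains, and only for smoking effects near 1 SD or more.
- *A reader might infer that all outcomes have standard errors that are too wide.* Section 4.1 allows up to four sites per participant, and section 13.1 records torque per site. Treating four sites as independent, with an assumed intraclass correlation of 0.3, gives a naive SE of 1/√(1 + 3 × 0.3) = 0.73 of the true one, the opposite direction. The net effect for site-level outcomes is unknown. The argument is cleanest for outcomes with one value per participant, such as the single biopsy.

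The calculations also cover only the normal-outcome linear model. No gain has been shown for stratified rank or exact tests, which draw little from a stratum of a few smokers.

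**Conclusion.** The mismatch is certain: smoking stratifies the allocation, and no planned between-group test uses it. The consequence is conditional. If smoking affects healing and strata are balanced, participant-level between-group tests are conservative and lose power. With 10 per arm, a normal outcome, a true effect of 1.32 SD and 2 to 10 smokers, the loss is about:

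- 0.5 to 2 points for a 0.5 SD smoking effect;
- 3 to 8 points for 1 SD (type I error about 2.7 to 4.1%);
- 6 to 18 points for 1.5 SD (type I error about 1.4 to 3.1%).

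If balance is not enforced, type I error is nominal, and power is lost from about 1 SD upward. In neither case is there bias or a raised false-positive risk. The change is worth making because it is nearly free under the balance that stratification is meant to achieve, and because fixing the analysis beforehand removes a later choice between adjusted and unadjusted results. Confidence is high on the mismatch and its direction, moderate on its size.

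**What to change.** Amend section 13.4 and the matching synopsis row as follows.

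- **Continuous outcomes:** compare groups with a linear model containing group and smoking stratum. Fit it to one value per participant or, where several sites are analysed, include a participant random effect or cluster term.
- **Non-normal outcomes:** use the stratified Wilcoxon (van Elteren) test.
- **Binary outcomes:** use an exact test stratified by smoking.
- **Sparse stratum:** state that the smoking term is dropped if there are no smokers, or smokers in only one arm.

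The cost is wording and one degree of freedom. Smoking status must already be known to stratify, so no new data are needed. Stating in section 4.2 how balance within strata is achieved would also settle which of the two cases above applies; without enforced balance, the term could cost up to about 2.7 points if smoking has no effect. The within-group paired tests and adjustment for baseline values are separate matters and are not addressed by this change.
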